Aim 1. Determine impact of DOMS pain on demand for alcohol and marijuana and examine race and sex as moderators of this relationship.

We predict that those who undergo the DOMS induction paradigm will show greater increases in alcohol and marijuana demand than participants in the sham DOMS control group. We also predict an interactive effect of race and sex on DOMS-related changes in alcohol and marijuana demand, such that increases may be greater in White men than Black women and men, as well as White women.

Aim 2. Identify psychosocial factors associated with change in demand for alcohol and marijuana after DOMS induction.

Consistent with current evidence,^{42, 67} we predict that pain-related negative affect will mediate the association between DOMS-related pain and increased demand for alcohol and marijuana. We also predict that greater expectancy of analgesia from marijuana or alcohol use, higher negative urgency, and history of self-medication behaviors will predict greater change in alcohol and marijuana demand.

6. Research Plan:

Participants

We will recruit participants aged 21 years and older who are regular co-users of alcohol and marijuana (i.e., concurrent or simultaneous use at least 2-3 times per week over the past 6 months). Extent of co-use will be determined using the Alcohol Use Disorders Identification Test (AUDIT) and Cannabis Use Disorder Identification Test, Revised (CUDIT-R). A research team member will inform participants of inclusion and exclusion criteria via email or the phone. If an individual believes they meet all study criteria, they will be scheduled for the first study session (see Phone and Email Scripts for details). We will review all inclusion and exclusion criteria one additional time with participants before initiating the Informed Consent process.

Inclusion/Exclusion Criteria

Detailed inclusion/exclusion criteria are provided in Table 1.

Table 1. Inclusion and exclusion criteria
Inclusion Criteria 
• Aged 21-65 years;• English-speaking• Self-identify as White/Caucasian or Black/African American• Own a smartphone with cellular/data plan• Regularly co-use alcohol and smoked marijuana as indicated by scores of ≥ 3 on item 1 of the CUDIT-R and AUDIT.• Willing and able to give informed consent

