Hypotheses for DOMS-related changes in alcohol and marijuana demand indices (persistence and amplitude) will be assessed using separate 2 (group: DOMS vs. sham DOMS) x 2 (sex: men vs. women) x 2 (race: White vs. Black) x 2 (time: visit 1 vs. visit 2) repeated measures analysis of variance (ANOVA). Identical ANOVAs will examine changes in marijuana demand indices.

Aim 2: Identify psychosocial factors associated with change in demand for alcohol and marijuana after DOMS induction.

To test the hypothesis that negative affect mediates the relationship between DOMS pain and increased alcohol and marijuana demand, Pearson correlations will be conducted to examine continuous relationships between measures of pain, pain-related negative affect (e.g. pain experience VASs), and change in alcohol and marijuana demand. A series of linear regressions will then be conducted to examine 1) the effect of group (DOMS vs. sham DOMS) on change in alcohol and marijuana demand, and 2) the effect of group and pain-related negative affect on change in alcohol and marijuana demand. We will test the significance of indirect effects of pain-related negative affect using PROCESS, a custom macro in SPSS.

To examine the hypothesis that greater expectancy of analgesia from marijuana or alcohol use, higher negative urgency, and history of self-medication behaviors will predict greater change in demand, a simultaneous multiple linear regression analysis will be conducted with these variables as predictors in the model.

Power Analysis

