Effect size estimates for this study were derived from an interim analysis of data from an ongoing pilot project that examined the effect of DOMS on alcohol demand (N=40). In our pilot work, alcohol demand was assessed using the Alcohol Purchase Task (APT) before and after DOMS induction. Amplitude and persistence were derived from APT data using principal components analysis,⁸³⁻⁸⁴ and these factors explained approximately 89% of the variance in alcohol demand metrics. Changes in amplitude and persistence were examined using separate 2 (group: sham vs. DOMS) x 2 (time: time 1 vs. time 2) x 2 (sex: men vs. women) repeated measures ANOVAs. Results indicated sex x group x time interactions for both factors, such that DOMS tended to increase amplitude in men and decrease amplitude in women, $F(1,36)=3.13$, $p=.09$, partial eta squared=.08. A similar pattern of effects was found for persistence where DOMS decreased persistence in women and increased persistence in men, $F(1, 36) = 14.55$, $p=.001$, partial eta squared=.29. With power analyses conducted in G*Power ($\alpha=.05$, power=.80, correlation between repeated measures=0.5), we expect that a proposed sample size of 56 participants will be sufficient to achieve the objectives of the proposed research and have adequate sensitivity to detect medium between-group and interactive effects for which we do not have preliminary data.

7. Possible Discomforts and Risks:

Psychological Discomforts and Risks. Participants may be reminded of unpleasant emotions or experience negative thoughts or bodily sensations while reporting aspects of their current psychosocial functioning or medical history. To mitigate this risk, all participants will be informed they can withdraw from the study at any time or skip individual questions that may be upsetting to them.

Induction of Muscle Pain using Exercise: There is a low risk that exertional rhabdomyolysis (breakdown of muscle tissue due to damage) and myoglobinuria (a large amount of muscle proteins in the urine) may occur following eccentric exercise. However, research suggests that this occurs primarily if a person had not consumed enough fluids before multiple muscle groups are exercised eccentrically.⁸⁷⁻⁸⁸ We will address this risk by instructing participants to remain well-hydrated 24 hours prior to DOMS induction.

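### N = 56 is called sufficient at a power setting of .80, but it gives only about 52–58% power for the pilot's own amplitude interaction (about 99% for persistence)

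*Combined protocol and SAP*

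**What the plan says.** Section 6, Power Analysis, opens with "Effect size estimates for this study were derived from an interim analysis of data from an ongoing pilot project" (N = 40, alcohol demand). It reports two sex x group x time interactions. For amplitude, "DOMS tended to increase amplitude in men and decrease amplitude in women, $F(1,36)=3.13$, $p=.09$, partial eta squared=.08". For persistence, F(1,36) = 14.55 and partial eta squared .29. It then lists the G*Power settings: alpha .05, power .80, correlation between repeated measures 0.5. From these it concludes that "we expect that a proposed sample size of 56 participants will be sufficient to achieve the objectives of the proposed research", and that there is "adequate sensitivity to detect medium between-group and interactive effects for which we do not have preliminary data".

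The paragraph does not say which effect size was entered, how many groups, how many numerator degrees of freedom, or which effect-size option was used.

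The Data Analysis Strategy for Aim 1 makes both factors outcomes: "Hypotheses for DOMS-related changes in alcohol and marijuana demand indices (persistence and amplitude) will be assessed" in a group x sex x race x time repeated-measures ANOVA. Aim 1 in Section 5 predicts that the DOMS group "will show greater increases in alcohol and marijuana demand than participants in the sham DOMS control group", and that race and sex jointly modify this effect.

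**The concern.** The pilot is the stated basis for the effect sizes, and .80 is the only power figure in the plan. A reader will therefore take 80% to apply to the amplitude interaction as well as to persistence. The pilot amplitude effect is much the smaller of the two and was not significant in 40 people. Adding 16 participants to an effect with F = 3.13 cannot plausibly bring power to 80%.

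If power for amplitude is little better than even, a non-significant amplitude result would be common even if the pilot effect were real. Anyone relying on the stated .80 could then read it as evidence of no effect. The claim about *medium* effects does not help, because it does not say how large a change in demand the study can detect.

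**Working it through.** **Inputs.** Alpha .05, power .80, r = 0.5, N = 56, and pilot F(1,36) = 3.13 and 14.55 (Power Analysis). Eight between-subject cells and two visits (Data Analysis Strategy, Aim 1). Assumed: 7 per cell and no dropout, since the documents give no figure for either.

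**Pilot effect sizes.** 3.13/(3.13 + 36) = .080 and 14.55/(14.55 + 36) = .288, matching the printed values. For amplitude, f² = .08/.92 = .0870 and f = .295.

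**Can 56 be reproduced?** Yes, by one route. Enter f = .295 in G*Power's default within-between option with 8 groups, 2 times and r = .5. Then λ = f² x N x 2/(1 − .5) = 4Nf², with df 7 and N − 8. Power is .791 at N = 48 and .803 at N = 49; rounding 49 up to a multiple of 8 gives 56 (power .871). This route counts the correlation twice, because f already contains it, and it tests a pooled 7-df effect. It is an inference: f = .25 with 8 groups and 3 df also gives 49. Nothing below depends on it.

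**Power on the pilot's own scale.** With two visits, each interaction with time is a 1-df test on change scores, with error df 56 − 8 = 48. Power comes from the noncentral F(1,48).

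| Conversion | λ, amplitude | Power, amplitude | Power, persistence |
|---|---|---|---|
| λ = 48f² | 4.17 | .517 | .991 |
| λ = pilot F x 56/40 | 4.38 | .536 | .993 |
| λ = 56f² | 4.87 | .580 | .997 |

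Simulation with 8 cells of 7 agrees: .535 for the direct rescaling and .581 for λ = 56f².

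**N for 80% on amplitude.** 93 (λ = f²N), 101 (λ = f²(N − 8)) or 103 (λ = 3.13N/40).

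**What N = 56 can detect.** Power of 80% at df 1 and 48 needs λ = 8.175. That is f² between 8.175/56 and 8.175/48, or partial eta squared of about .13 to .15, against .08 in the pilot. In SDs of the change score:

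- Group x time: √(8.175 x 4/56) = 0.76. As the SD of change is √(2(1 − r)) single-visit SDs, this is 0.76 single-visit SD at r = .5, 0.90 at r = .3 and 0.59 at r = .7.
- Sex difference in the DOMS effect: √(8.175 x 4/14) = 1.53. The pilot values, assuming 10 per pilot cell, are √(3.13 x 4/10) = 1.12 for amplitude and √(14.55 x 4/10) = 2.41 for persistence.
- Four-way contrast: √(8.175 x 8/7) = 3.06.

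**The *medium* claim.** Suppose it means f = .25 on the default scale. Then λ = 4 x 56 x .0625 = 14 and a 1-df interaction with time has 96% power. At r = .5, however, that f is a difference in change of √(14 x 4/56) = 1.0 SD for group x time, √(14 x 4/14) = 2.0 SD for the sex difference and √(14 x 8/7) = 4.0 SD for the four-way contrast. A group x time difference of 0.5 SD gives λ = 3.5 and 45% power.

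**Dropout.** With an assumed 50 completers (error df 42), amplitude power is 46–53%.

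**The case against.** Four objections deserve weight.

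- **The plan never says 80% for amplitude.** It lists software settings and then states an expectation about the objectives. That is literally so. But the same paragraph offers the amplitude effect as a basis for sizing, and it reserves *medium* for effects without pilot data, so amplitude is not excluded from the claim of sufficiency.
- **Sex x group x time is not a named Aim 1 prediction.** The named ones are group x time and the joint effect of race and sex. This is right, and detectable differences for those effects should be stated too. The sex interaction is still a term in the planned ANOVA and the only kind of effect for which the plan gives pilot estimates.
- **52–58% suggests too much precision.** The range reflects only how the effect size is converted. A 95% interval for the pilot amplitude noncentrality includes zero and reaches a partial eta squared of about .26, so implied power runs from about 5% to 99%. For persistence the same exercise gives about 48% to nearly 100%. This stands as a caution on both figures. It does not rescue the claim, because the plan itself chose the pilot point estimates.
- **The double-counting route is not the only one leading to 56.** Correct, which is why the conclusion does not rest on it. That the calculation cannot be identified is itself a reason to name it.

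**Conclusion.** The concern holds. On the plan's own basis, N = 56 gives about 52–58% power for the pilot amplitude interaction, well short of .80, and about 99% for persistence. This assumes two-sided alpha .05, equal cells, no dropout, and the pilot estimates taken as true; dropout would lower the figures. The *medium* claim is not shown to be wrong, but without a number it cannot be checked. The paragraph should be corrected. The design need not change.

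**What to change.** Keep N = 56 and replace the claim of sufficiency with a sensitivity statement that:

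1. names the test (1-df interaction with time in the 2 x 2 x 2 x 2 ANOVA, error df 48) and the effect-size option, which must match a partial eta squared from a repeated-measures F;
2. gives power of about 99% for the pilot persistence interaction and about 52–58% for the pilot amplitude interaction, both labelled as conditional on the estimates from 40 people;
3. gives the group x time difference detectable with 80% power, about 0.76 SD (equal cells, r = .5, no dropout), in place of the unquantified *medium* claim. It would help to add 1.53 SD of change for the sex difference in the DOMS effect and about 3.06 SD for the four-way contrast.

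The cost is wording only; sample size, outcomes and analyses stay as they are. The drawback is that the stated power becomes less favourable.
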